12) Partners Collaborative Media (PCM) will provide oversight (for a fee) to ensure that the clinical and movement disorders assessments taking place every two weeks using skype-like video conferencing are secure. Specific web cameras recommended by PCM will be used by McLean staff and by the subjects. All calls will be initiated from McLean using a Partners computer. This computer will have the Cisco program, "blue jeans," installed. PCM will create generic credentials for the subjects such that they will not be using their own actual skype credentials. Thus, if the skype material is stolen, it cannot be linked to the subjects themselves. A McLean clinician will call the subjects by clicking on customized phone numbers and allow the McLean caller to lock the virtual meeting room.

A technical statement from PCM about how the secure connection is implemented has been uploaded.

VI. Biostatistical Analysis

All data acquisition and processing will be carried out blind to mutation status. The McLean investigators have extensive imaging databases involving controls and patients with psychotic disorders. Thus, we are well positioned to compare MRS spectra between carriers and non-carriers even if formal statistical testing is not always possible. At a minimum, using data from groups scanned on the same scanners under the same conditions, we can establish where our subjects fall in the range of values compared with other subject groups using z-scores or % difference scores (e.g., Glu, GABA, Gln metabolite levels; Gly and other metabolite concentrations; Gln:Glu ratios). It will be possible to assess the magnitude of change in clinical and neurocognitive function and to correlate change in amino acid levels with clinical and neurocognitive change scores during DCS vs placebo. This is not a population study; it is designed to provide mechanistic insights about the effects of this mutation in the brain. [name] has PERG data on other patients and on controls.

VII. Risk and Discomforts

The imaging procedures have been used extensively at McLean without complications and subjects will be carefully screened.

The procedures described above pose no serious physical risk to subjects and no psychological, social, or legal risks are anticipated.

Although there are no known general risks associated with MRI scans, there are risks to individual subjects who have contraindications to MRI scanning, including those with metal implants in their body (pacemaker, aneurysm clips, metal screws and plates for orthopedic purposes, hearing implants, certain kinds of tattoos, sheetmetal workers with lodged metal fragments in the eyes). Subjects are screened carefully and excluded if there are even suspected contraindications to scanning. All subjects are asked to remove jewelry, belts and other metal-containing objects. Surgical records will be retrieved prior to scan for subjects who have had metal placed in their body intra-operatively to ensure the hardware is MRI safe, even if the subject has been told the hardware is MRI-safe or if they have had MRI scans since the operation. As an additional precaution, subjects are screened with a handheld metal-detection wand prior to the scan to ensure that no unidentified metal objects remain on the subject. The noise generated by the pulsing of the gradients can lead to temporary decrease in hearing. The use of disposable earplugs is an easy and reliable means of preventing hearing loss. The risks associated with Specific Absorption Rate (SAR) are related to the fact that given a large enough SAR, heating of the tissue may occur. These experiments will comply with all FDA guidelines with regard to RF power deposition. There is also the potential risk of injury from a projectile (i.e., ferromagnetic objects being attracted into the magnet); and of asphyxiation due to large amounts of cryogenic gases generated during a quench (i.e., the event which occurs when a magnet makes the sudden transition from superconducting to resistively conducting). Routine safety procedures are in place at both scanning centers to screen subjects prior to scanning, maintain security of the restricted access areas, and ensure that system security features are in good working order. Both imaging centers associated with this study (McLean, NKI) are very experienced with MRI scanning and have impeccable safety records. The effects of MRI on the fetus are not well characterized. Therefore, females of childbearing age must be sexually inactive or be using a contraceptive measure for three months prior to being scanned.

The scans involve use of a standard clinical MRI scanner (3T) as well as a high field (4T) MRI scanner. The 4T scanner is not used for routine clinical studies in children or adults, but the FDA has determined (July 14, 2003) that scanners with magnetic field strengths of less than 8 Tesla do not represent a significant risk to adults, children, or infants older than 1 month.¹⁶⁴ Most people experience no ill effects from 3T or 4 T scans, but some do report claustrophobia, dizziness, mild nausea, headaches, a metallic taste in their mouth, back tingling, double vision, or sensation of flashing lights. These symptoms, if present, disappear shortly after leaving the scanner. During the scan, the examiner can see and hear the subjects and will ask them to report any problems so the scan can be stopped if necessary. A magnetic resonance scan may be uncomfortable due to claustrophobia, lying still for an hour, or loud sounds. Subjects who express serious concern about these will not be included. The scan will be stopped if the subject expresses discomfort. Total time in the scanner for the structural scan and 2 MRS scans at McLean is 150 minutes, with breaks occurring between scans (structural: 15 minutes; MEGAPRESS: 60 minutes; J-PRESS: 75 minutes). Subjects will be allowed to leave the scanner between scans and can be re-positioned for the next scan, as described in the application. Both subjects have successfully completed imaging procedures.

DCS has been widely used to augment standard psychotropic drug treatment and is well tolerated. The daily dose of 50 mg is low enough to be a partial agonist of the GMS and has no side effects. The subjects will be monitored closely by the research team and by their own psychiatrists. Blood chemistries, including liver/kidney function tests, will be monitored at baseline and at the end of each treatment arm.

Periodic blood samples involve the slight discomfort of a needle stick and the small risk of a bruise. Every attempt is made to have the subject feel comfortable and at ease with the environment and the staff.

The eye exam procedures are routine and should cause minimal or no discomfort.

Risks to privacy and confidentiality are minimal. All subjects are assigned a random 4-digit ID number, which is used to code all material.

VIII. Potential Benefits

The general goal of this study is to clarify the neurobiology of a mutation in glycine mutation and to determine whether carriers of this mutation may preferentially benefit from DCS augmentation of their medication regimen. Although subjects receive no immediate benefit from the brain imaging procedures beyond contributing to important research and reasonable monetary compensation for the time commitment, the potential scientific yield could have a major impact on identifying causal mechanisms in psychotic disorders. If the DCS augmentation is beneficial, these two subjects may experience a significant reduction in psychotic symptoms and improvement in neurocognition, which may also help other subjects with mutations impacting the glycine metabolic pathway and NMDA receptor function.

IX. Monitoring and Quality Assurance

The scientific integrity of the study and protection of participant safety will be monitored by the investigators using an Adverse Event Tracking Log, including the detection and reporting of adverse events. The safety data include all imaging procedures, the neurocognitive function battery, as well as the double-blind placebo-controlled and open-label DCS augmentation trials. Efficacy data includes all DCS-related procedures.

All adverse events will be promptly reported to the Partners Human Research Committee (PHRC) and NIMH as appropriate. At a minimum, the investigators will review all adverse events at the end of each treatment arm, but more often if needed. Unanticipated problems involving risks to subjects or others including adverse events will be reported to the PHRC in accordance with PHRC unanticipated problems reporting guidelines.

At a minimum, the investigators will review all adverse events at the end of each treatment arm, but more often if needed. The research will be altered or stopped if subjects have adverse reactions to any of the procedures (e.g., claustrophobia in the scanners) or significant side effects to DCS.

The subjects will also be given emergency contact numbers for Drs. [name], [name], [name], and [name]. The subjects will also be told to go the nearest emergency room if they experience any acute side effects (e.g., vomiting, diarrhea). [name], a consultant on this project, has a great deal of experience in using DCS to augment the therapeutic effects of antipsychotic medication and will be available to advise the study team about any needed changes (i.e., dose reduction, discontinuation) based on side effects or changes in clinical state. Decisions about how best to proceed will be made in consultation among Drs. [name], [name], ([name] if [name] is not available), [name], and the McLean pharmacist. Based on [name] extensive experience

using this dose of DCS, it is very unlikely that it will be necessary to discontinue the trial altogether. Should there be changes in any arm of the study, such as temporary discontinuation or extending the time period, the IRB will be notified. If subjects develop side effects that make them too uncomfortable or that make it medically necessary to discontinue the study, the study will be stopped. This level of oversight for subjects who are not local seems reasonable for monitoring subjects taking a compound that has been safely used as an augmentation strategy. The same procedures were used in the initial glycine augmentation study and the current extended glycine trial and have worked effectively.

The PI has talked all of the people involved in the study (Drs. [name], [name], [name], [name], [name], and [name]; [name]) about the adequacy of the plan to provide medical and/or psychiatric monitoring of these patients while they are taking a novel compound; they have agreed that the proposed plan is acceptable. [name] is the psychiatrist for one of the subjects and [name] is the psychiatrist for the other. Blood work results are faxed to them and they are kept apprised of any notable developments (e., beginning and end of any phase of the study, worsening of clinical state, improvement in clinical state). They, in turn, contact the PI if they become concerned about changes in clinical state or side effects.

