## EQUITABLE SELECTION OF SUBJECTS

The risks and benefits of the research must be fairly distributed among the populations that stand to benefit from it. No group of persons, for example, men, women, pregnant women, children, and minorities, should be categorically excluded from the research without a good scientific or ethical reason to do so. Please provide the basis for concluding that the study population is representative of the population that stands to potentially benefit from this research.

The only scientific and ethical justification for including subjects in this study is if their participation can help to clarify the neurobiology of a mutation in glycine metabolism and if they might benefit from DCS augmentation. All other subjects are excluded. Therefore, the only eligible participants at the present time are two carriers of this specific genetic mutation who also have a diagnosis of a psychotic disorder and have participated in the Neurobiology of a Mutation in Glycine Metabolism in Psychotic Disorders (2012P001597) protocol. To our knowledge, this is a private mutation although different mutations in the same gene have been reported in other individuals with psychotic disorders and with autism spectrum disorders. These individuals may be potentially eligible for a similar augmentation intervention.

When people who do not speak English are excluded from participation in the research, provide the scientific rationale for doing so. Individuals who do not speak English should not be denied participation in research simply because it is inconvenient to translate the consent form in different languages and to have an interpreter present.

N/A

For guidance, refer to the following Partners policy:

Obtaining and Documenting Informed Consent of Subjects who do not Speak English

[https://partnershealthcare-public.sharepoint.com/ClinicalResearch/Non-English\\_Speaking\\_Subjects.1.10.pdf](https://partnershealthcare-public.sharepoint.com/ClinicalResearch/Non-English_Speaking_Subjects.1.10.pdf)

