## RECRUITMENT PROCEDURES

Explain in detail the specific methodology that will be used to recruit subjects. Specifically address how, when, where and by whom subjects will be identified and approached about participation. Include any specific recruitment methods used to enhance recruitment of women and minorities.

The subjects will be selected on the basis of having a triplication of the GLDC gene, a mutation involving an abnormality in glycine metabolism that may be implicated in psychotic disorders, a psychotic disorder, and having participated in the Neurobiology of a Mutation in Glycine Metabolism in Psychotic Disorders (2012P001597) protocol. Prior to beginning the study, the PI will call the subjects and review all of the procedures and time frames. The subjects will be flown to Boston for the McLean procedures and to Minneapolis for the UMN procedures. Other procedures will be carried out in the subjects' city of residence. The procedures will be scheduled well in advance to minimize inconvenience to the subjects and to optimize successful data collection at McLean.

Provide details of remuneration, when applicable. Even when subjects may derive medical benefit from participation, it is often the case that extra hospital visits, meals at the hospital, parking fees or other inconveniences will result in additional out-of-pocket expenses related to study participation. Investigators may wish to consider providing reimbursement for such expenses when funding is available

Each subject will be paid \$1,000 for completing the open-label DCS study and \$1,000 for completing the entire double-blind DCS-placebo study. They will each be paid \$200 for the UMN procedures. The imaging, electrophysiology procedures will involve at least 1 week away from work other responsibilities. All expenses incurred as part of participating (e.g., travel, hotel, local transportation, and meal costs) will be paid for by the grant supporting this study. Subjects will be paid a pro-rated amount if unable to complete all procedures based on the proportion of the study that was completed. For example, if a subject completes 80% of the procedures, that subject would be paid \$800. Any additional expenses related to participation, such as gas or taxis, up to \$500.00 in year 1 and up to \$300 in year 2, will be reimbursed based on submitted receipts.

For guidance, refer to the following Partners policies:

Recruitment of Research Subjects

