## **PRIVACY AND CONFIDENTIALITY**

Describe methods used to protect the privacy of subjects and maintain confidentiality of data collected. This typically includes such practices as substituting codes for names and/or medical record numbers; removing face sheets or other identifiers from completed surveys/questionnaires; proper disposal of printed computer data; limited access to study data; use of password-protected computer databases; training for research staff on the importance of confidentiality of data, and storing research records in a secure location.

**NOTE:** Additional measures, such as obtaining a Certificate of Confidentiality, should be considered and are strongly encouraged when the research involves the collection of sensitive data, such as sexual, criminal or illegal behaviors.

Each subject will be assigned a 4-digit randomly generated ID number. All scans and blood samples will be labeled with this ID number. Signed consent forms and demographics forms with identifying information will be kept in locked file cabinets stored in a secure location with access limited to Drs. [name], [name], or [name]. Computer databases are password protected.

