The broad specific aims of this study are 1) to treat the carriers of this mutation with an NMDAR modulatory compound that can be administered as a pill, D-cycloserine (DCS), and 2) to compare the clinical and neurobiological changes achieved with DCS to those achieved with Gly. If the subjects experience similar clinical benefits, DCS augmentation could potentially be a long-term treatment for these individuals.

Specific Aim 1: To assess the acute (8 weeks) effects of open-label DCS augmentation on positive, negative, and mood symptoms and on neurocognition. Hypothesis: Improvement during acute and chronic treatment, but not during placebo. Greater improvement on DCS than on Gly. To assess changes in the same clinical and cognitive dimensions just mentioned during discontinuation of DCS and DCS treatment (6 weeks/arm).

Specific Aim 2: To assess the acute (8 weeks) effects of DCS augmentation on brain structure (3.0 Tesla) and chemistry using magnetic resonance spectroscopy (MRS, 4.0 Tesla). Hypothesis: Normalization of brain Gly level, decreased baseline GABA and increased baseline glutamate (Glu). Greater normalization on DCS than on Gly.

Specific Aim 3: To assess the acute (8 weeks) effects of DCS augmentation on auditory evoked response potentials (ERPs). Hypothesis: Greater normalization of P50, mismatch negativity (MMN), P300, gamma oscillations on DCS than on Gly.

Specific Aim 4: To assess the acute (8 weeks) effects of DCS augmentation on NMDAR in retinal ganglion cells. Hypothesis: Pattern electroretinogram amplitudes will increase more (i.e., greater saturation) on DCS than on Gly.

Specific Aim 5: To assess the acute (8 weeks) and subsequent (6 weeks) effects of DCS augmentation or placebo on amino acid levels and other metabolites (e.g., kynurenic acid, KYNA). Hypothesis: Serine and Gly levels will increase, and KYNA levels will decrease, more on DCS than on Gly, and more on DCS and Gly than on placebo.

III. Subject Selection

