Optical coherence tomography (OCT): The OCT test uses light to measure structures in the eye. This machine also takes a picture of the inside of the eyes with a specialized camera. A trained photographer will conduct this test. The subject will sit in front of the OCT machine and be asked to look at a target. The head and chin will rest against a head rest and chin rest. The OCT machine will shine a light into the eye and a photograph will be taken. The test takes about 1-2 minutes per eye. This procedure is non-contact, FDA approved, and no risks are known to be associated with it other than the dilation.

Dilation drops may need to be applied to the eyes twice in each visit if the dilation effects wear off before all procedures are completed. There should be no additional risk associated with a second application of dilation drops.

During week 8:

- a) Weight measurement
- b) Repeat physical exam and EKG ([name], at McLean)
- c) Blood work (66 cc and 61 cc) (drawn in the Clinical Laboratory at McLean Hospital; frozen plasma for amino acid and psychotropic blood levels will shipped to the Analytical Psychopharmacology Laboratory at the Nathan Kline Institute (NKI) for processing (routine laboratory tests, such as CBC with differential, etc as well as DCS levels will be performed by North Shore Medical Center).
- d) Movement disorders assessment (extrapyramidal side effects, tardive dyskinesia - AIMS/SAS – by [name] or [name], in person at McLean)

- e) MCCB (MATRICS) - by [name], in person.
- f) EEG – [name], at McLean

f) Structural MRI (3T - 15 minutes), proton ¹H MRS (4T) for GABA and glutamate levels (MEGAPRESS - 1 hour); Proton ¹H MRS (4T-J-Resolved) for glycine levels (1 hour). All scan procedures are approved by the McLean IRB. All of these are brain imaging scans that were previously performed at McLean Hospital as part of the glycine study baseline procedures.

Subjects will first receive an occipital cortex echo time averaged (TEAV) MRS scan; an MRS technologist will provide oversight. Head and MRS voxel position coordinates at will be determined using brain structural landmarks and will be recorded.

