In addition, since both subjects will be taking DCS during the open-label phase, they will receive one MRS scan for glycine levels prior to their dose of DCS (above), followed by a scan shortly after taking the daily dose (50 mg) (90 minutes). We will be able to compare brain uptake after an acute dose (baseline) and after chronic treatment, including uptake immediately after dosing.

Subjects will first receive a baseline occipital cortex echo time averaged (TEAV) MRS scan; an MRS technologist will provide oversight. Head and MRS voxel position coordinates at will be determined using brain structural landmarks and will be recorded. After their DCS dose, subjects will be re-positioned in the scanner for the brain and blood measurements over the next two hours, as described above.

Clinical Oversight:

The subjects are well known to the PI and study staff, who will be in touch with them by phone on a weekly basis or more often as needed. Both subjects' psychiatrists will also be monitoring their clinical states and side effects. [name] will inform [name] and [name] immediately if any side effects or clinical changes are reported that warrant medical follow-up.

At the end of the first week of DCS, and at the end of weeks 3 and 5 (more often if necessary), the subjects will be called by a study physician ([name]) to assess how they are reacting to the DCS. The subjects will also be given emergency contact numbers for Drs. [name], [name], and [name]. The subjects will also be told to call [name] immediately if they experience any acute side effects (e.g., exacerbation of psychotic or negative symptoms).

Week 9 will be a washout week during which neither DCS nor placebo will be administered.

5) 6 Weeks on DCS (50 mg/d) or Placebo (weeks 10-15) – Treatment Arm B.

The McLean Pharmacy will prepare and label prescriptions for DCS capsules, Placebo capsules, and vitamin B-12 Complex tablets, which will be FedEx'ed in 4-6-week supplies. The placebo is supplied in opaque gelatin capsules filled with microcrystalline cellulose. The McLean Hospital Pharmacy will provide the placebo.

Subjects will keep a daily log to mark the time each dose was taken.

At the end of weeks 11, 13, and 15:

Clinical ratings as described above using "skype-like" video conferencing.

At the end of week 12:
Blood work as described above.
Weight measurement.

An assessment of movement disorders (extrapyramidal side effects, tardive dyskinesia - AIMS/SAS - [name], by "skype."

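### The SAP blinds data processing only to mutation status, which is constant and known in both subjects, and specifies no blind to treatment session for the DCS-versus-glycine MRS, ERP and ERG contrasts of Aims 2-4

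*SAP*

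**What the plan says.** SAP section VI (Biostatistical Analysis) opens with the rule: "All data acquisition and processing will be carried out blind to mutation status". It then turns to comparing the subjects' spectra with those of non-carriers in existing databases, by z-scores or percentage differences, and mentions pattern-ERG data held on other patients and controls. Treatment, visit and session do not appear in the blinding rule.

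The Protocol, under Equitable Selection of Subjects, states that "the only eligible participants at the present time are two carriers of this specific genetic mutation". Its Recruitment Procedures add: "The subjects will be selected on the basis of having a triplication of the GLDC gene". The SAP's clinical oversight text for Treatment Arm A says: "The subjects are well known to the PI and study staff".

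The hypotheses in SAP section II are directional and set DCS against glycine. For brain structure and chemistry (Aim 2): "Greater normalization on DCS than on Gly". For auditory evoked responses (Aim 3): "Greater normalization of P50, mismatch negativity (MMN), P300, gamma oscillations on DCS than on Gly". Aim 4 expects pattern-ERG amplitudes to rise more on DCS than on glycine.

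On coding, the Protocol's Privacy and Confidentiality section says of each subject's four-digit number: "All scans and blood samples will be labeled with this ID number".

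**The concern.** A blind protects a comparison only if it hides the factor being compared. In Aims 2-4 that factor is the treatment session: on DCS or on glycine. The stated blind hides something else, and that something does not vary between the two people enrolled.

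A reader of the SAP would take the rule, which claims to cover all acquisition and processing, as protection for every measurement in the study. For Aims 2-4 it is not. The hypotheses name the expected direction in advance, there are two subjects, and the SAP itself accepts that formal testing will not always be possible. The conclusions will therefore rest on the direction and size of change in two people. Any choice made during processing by someone who knows which file is the DCS session could tilt that result, and the plan as written offers no stated safeguard.

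**Working it through.** No calculation applies. The SAP states no sample size, error rate or decision rule for these contrasts, so the check is to set the passages side by side.

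**1. What the stated blind can hide**

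| Comparison | Factor that differs | Hidden by a mutation-status blind? |
|---|---|---|
| Carriers versus database non-carriers (SAP VI) | Mutation status | Yes, if files are mixed before processing |
| DCS versus glycine, same subjects (Aims 2-4) | Treatment session | No; mutation status takes one value throughout |

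**2. When the DCS data are collected.** The Protocol's study procedures and SAP Treatment Arm A agree. The ERG is at the end of week 7, and the structural MRI, MRS and EEG are in week 8, all during open-label DCS. These are the only points at which the available text schedules those procedures explicitly.

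**3. Whether another blind reaches those sessions.** The design description before SAP section II keeps subjects and all staff except the pharmacist unaware of drug or placebo. That applies to the four six-week randomised periods, which start in week 10 after a washout in week 9. Weeks 7-8 fall before it.

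**4. Where the comparator comes from.** The Protocol takes baseline imaging from the earlier glycine study. SAP Treatment Arm A says of the week-8 scans: "All of these are brain imaging scans that were previously performed at McLean Hospital as part of the glycine study baseline procedures". The comparison is therefore with sessions from another study, not with a concurrent masked session.

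**5. Whether the coding masks session.** The ID number is assigned per subject. It protects identity, and no separate session code is described. This alone does not show that session is visible at processing; it shows only that nothing is stated to hide it.

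**6. Whether acquisition can be blind.** The subjects are selected as carriers, flown in for these procedures and familiar to study staff. In week 8 a glycine scan precedes the daily dose, and the subject is re-positioned in the scanner after it. Staff running that session would ordinarily know both facts.

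**7. Extent.** Aims 2, 3 and 4 are three of the five specific aims. With one DCS visit per modality, each measure gives 2 subjects × 1 DCS-minus-glycine difference = 2 differences, apart from the repeat scans around the dose in week 8.

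**The case against.** Several points on the other side have force.

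- **The blind has a purpose.** A reader might infer that the plan chose the wrong factor. It did not: mutation status varies in the database comparison that SAP VI goes on to describe. The blind is incomplete and should be kept for processing.
- **Silence is not proof.** A reader might infer that every DCS-versus-glycine contrast will be processed unblinded. No passage says so. Open-label dosing does not prevent masked processing, and how the glycine sessions were processed belongs to the earlier protocol, which is not among these documents. Parts of the SAP were also missing from the text reviewed. However, the Biostatistical Analysis section is present, and its rule claims to cover all data.
- **Not every operator need know.** The documents show that the PI and study staff know the carriers. They do not show what each scanner, EEG or ERG operator knows. This supports doubt about blind acquisition, but does not prove it impossible for every person.
- **Discretion in processing is undocumented.** The steps for spectra, ERPs and ERGs are not described in the available text. The J-resolved spectroscopy work cited is model-based fitting, which may leave less room for judgement than manual reading.
- **On-glycine files may not be available.** Aims 2-4 imply that on-glycine measurements exist, and the SAP says both subjects have completed the eye procedures twice. The imaging statements, though, refer only to glycine-study baseline scans.
- **A larger limitation remains.** This is a two-person mechanistic study comparing open-label sessions with earlier ones. Masked processing does not change that.

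These points narrow the finding. None supplies a session blind for Aims 2-4.

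**Conclusion.** The concern holds in this form: the only blind specified for measurement data is to mutation status. It suits the carrier-versus-non-carrier comparison, but gives no protection to the within-subject DCS-versus-glycine contrasts for MRI/MRS, ERP and ERG. The double-blind phase does not fill the gap. The claim that acquisition is blind is not credible as a general statement for known carriers attending open-label visits.

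The documents do not support saying that processing will in fact be unblinded, nor do they allow the bias to be quantified: they give no processing detail, no variability and no rule for declaring a hypothesis met. The conclusion assumes that no session blind is stated in the SAP text that was unavailable or in the earlier glycine protocol. The change is worth making because it is cheap and the affected results rest on two people, but it does not bear on the study's feasibility.

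**What to change.** In SAP section VI, keep the mutation-status blind for processing and add a session blind:

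- Before processing, someone who will not do the processing removes subject ID and date from the MRS, structural MRI, EEG and ERG files and assigns random codes.
- The week-7 and week-8 DCS files are mixed with whatever archived glycine-study sessions of the same subjects, and whatever control files, are available. The SAP should list which these are.
- All files are processed with one pipeline version.
- Values are locked before the codes are broken.

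Drop the statement that acquisition is blind, or limit it to named functions whose operators are in fact unaware of mutation status.

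The cost is SAP wording, file recoding and rerunning archived sessions. No visit, dose or procedure changes. The downside is that results wait until the batch is complete.

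### SAP VI places two individual carriers against reference groups by plain z-scores or % differences, which treat the group mean and SD as known; a single-case t with the reference n and an interval would be more exact.

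*SAP*

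**What the plan says.** The Protocol (Equitable Selection of Subjects) states that "the only eligible participants at the present time are two carriers of this specific genetic mutation". The comparison with other people is described in SAP section VI, Biostatistical Analysis. It starts from the archive: "The McLean investigators have extensive imaging databases involving controls and patients with psychotic disorders". It accepts that carriers and non-carriers may be compared "even if formal statistical testing is not always possible", and then sets a floor for what will be done: "we can establish where our subjects fall in the range of values compared with other subject groups using z-scores or % difference scores". Only some of the archive qualifies for this, because the placement is to be made "using data from groups scanned on the same scanners under the same conditions". The examples of measures that it lists are "Glu, GABA, Gln metabolite levels; Gly and other metabolite concentrations; Gln:Glu ratios".

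The section gives no size for any matched reference group, no matching rule beyond scanner and conditions, no cut-off for calling a value abnormal, and no interval. It also says: "This is not a population study; it is designed to provide mechanistic insights about the effects of this mutation in the brain".

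Specific Aim 2 (SAP section II) hypothesises that brain glycine will normalise, and will do so more on DCS than on glycine.

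**The concern.** A z-score for one person is exact only if the reference mean and SD are known. Here both are estimated from a sample, and the statistic ignores that error. A % difference does not use the reference SD at all, so it cannot show how unusual a value is.

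The word extensive describes the archive, not the matched group. SAP section V, under the week 8 procedures, obtains glycine from a J-resolved 4T acquisition and GABA and glutamate from a separate MEGAPRESS acquisition. SAP section VII notes that the 4T scanner is not in routine clinical use. The usable n could therefore differ by metabolite and be well below the archive total.

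What is at stake is the accuracy of statements about where each carrier lies. With two subjects, nothing averages out a misplaced value, and describing a level as normalised presupposes some reference range.

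**Working it through.** **Inputs.** There are two carriers (Protocol, Equitable Selection of Subjects). The method is a z-score or % difference (SAP VI). The reference n is not given, so n = 10, 20 and 50 are assumed, with the range extended to find where the effect becomes small. No cut-off is given; |z| > 1.96 is assumed as a convention for one part of the check. Normality is assumed. The plan states no figure of its own to reproduce.

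**Formula.** Let x be a carrier's value, and let the mean and s come from n reference subjects. If the carrier belongs to the same normal population, then

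t = (x - mean)/(s × sqrt(1 + 1/n)) = z/sqrt(1 + 1/n)

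follows a t distribution on n - 1 df. The plain z omits the factor sqrt(1 + 1/n) and uses normal tails in place of t tails.

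**Descriptive reading (no cut-off needed).** Take z = -2. The normal tail is 2.3%. The estimated tail is P(t on n - 1 df > 2/sqrt(1 + 1/n)):

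| n | 2/sqrt(1 + 1/n) | estimated tail |
|---|---|---|
| 10 | 1.907 | 4.4% |
| 20 | 1.952 | 3.3% |
| 50 | 1.980 | 2.7% |

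**Reading with an assumed |z| > 1.96 convention.** The rate at which a non-unusual carrier falls outside is 2 × P(t on n - 1 df > 1.96/sqrt(1 + 1/n)). The cut-off on the z scale that restores 5% is t(0.975, n - 1) × sqrt(1 + 1/n):

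| n | rate (nominal 5%) | cut-off for 5% |
|---|---|---|
| 10 | 9.4% | 2.37 |
| 20 | 7.1% | 2.14 |
| 30 | 6.4% | 2.08 |
| 50 | 5.8% | 2.03 |
| 100 | 5.4% | 1.99 |

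Simulation for n up to 50 agreed with the formula to within 0.1 point. The excess over 5% is 1 point or less from n = 41 and 0.5 point or less from n = 80.

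**% difference.** This is 100 × (x - mean)/mean = 100 × z × (s/mean). The same % difference is common or rare depending on s/mean, which the score does not show.

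**Price of the correction.** At n = 10, a value truly 2.5 SD from the population mean passes |z| > 1.96 in 86% of reference samples, and passes the corrected cut-off of 2.37 in 63% (simulation).

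**The case against.** The best defence is that the SAP makes no test here. It describes position in a range, disclaims population inference, and calls z-scores a minimum, which leaves room for formal testing. If the matched groups are as large as an extensive archive suggests, the correction is negligible. Part of the SAP was not in the text reviewed, so a stated n cannot be ruled out. Most of this stands and limits the size of the point. It does not remove it, because saying where a subject falls in a range is itself a percentile statement, and plain z shifts that percentile even without a cut-off.

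A reader might infer stronger conclusions, which the documents do not support:

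- **That the z-score decides whether a carrier is abnormal.** SAP VI sets no cut-off and no abnormality rule. The 1.96 figures rest on an assumed convention.
- **That the error always exaggerates abnormality.** It does so on average. In simulation, 37% of reference samples at n = 10 give a true rate below 5%. A larger |z| also makes a treated value look less normal, which works against the Aim 2 hypothesis.
- **That the comparison of DCS with glycine is compromised.** Against one reference group, the t divides every z by the same constant, so the ordering of a subject's sessions does not change.
- **That many measures make a false finding likely because of plain z.** That is mainly multiplicity, which the t leaves in place. With five independent measures and a known mean and SD, the chance of at least one value beyond 1.96 is already 1 - 0.95^5 = 22.6%. The listed measures are not independent either, since Gln:Glu is built from two of the others.

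**Conclusion.** The point holds as a modest matter of precision. Assuming normality, and on average over reference samples, a plain z overstates how extreme a carrier is at every finite n, and a % difference says nothing about rarity. The size depends on an n that the reviewed text does not give. At n = 10 the nominal 5% nearly doubles; above about 40 the excess is about 1 point or less. Skewed measures, such as a ratio, would change these figures. The point does not undermine a declared mechanistic study of two people.

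**What to change.** In SAP VI, replace the choice between z-scores and % difference scores with the single-case t, (x - mean)/(s × sqrt(1 + 1/n)) on n - 1 df. For each measure, report the matched reference n and a 95% interval for the carrier's percentile. Keep % difference as a supplement only. If repeat scans exist in the archive, change between one subject's sessions could also be judged against the test-retest SD. This is optional, because the reviewed text does not document such scans.

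The main change is a short edit that uses the same data and converges to z as n grows. It has a cost: at small n, fewer values will appear extreme, including some that truly are (63% rather than 86% for a value 2.5 SD out at n = 10, under the assumed convention).
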